4.2.1.1.7 Ongoing

Ongoing is derived from the last daily intensity of the solicited period computed as described in Section 4.2.1.1.1 and the maximum intensity on the ongoing period. The investigator's ongoing flag is not used because the measurement would determine the ongoing status of the reaction.

- Ongoing: If the last daily intensity of the solicited period is at least Grade 1 and the maximum intensity on the ongoing period is at least Grade 1.
- Not ongoing: If the last daily intensity of the solicited period is None or the maximum intensity on the ongoing period is None.
- Missing: all other conditions (in this case, it is not included in the denominator of the ongoing analysis in safety tables).

4.2.1.2 Unsolicited AEs

4.2.1.2.1 Presence

An observation will be considered an event if it has at least a verbatim term and is not a Grade 0 intensity event.

Grade 0 events are not included in safety analysis but are included in separate listings.

4.2.1.2.2 Intensity

Intensity will be derived according to the following classification: None, Grade 1, Grade 2, Grade 3, or Missing.

If the unsolicited AE is measurable and its preferred term is part of the list of solicited reactions, then the measurement is derived based upon and following the same rule of the intensity scales defined in the protocol for that measurable injection site or systemic reaction.

Intensity for the other unsolicited AEs will correspond to the value reported in the CRF.

The maximum intensity corresponds to the highest intensity for a unique term.

4.2.1.2.3 Last Vaccination

Last vaccination before an unsolicited AE is derived from the start date of the unsolicited AE provided in the CRF and is calculated as follows:

- If an unsolicited AE has a complete start date and different to any of the vaccination dates, the start date is used to determine the last vaccination before the unsolicited AE
- If an unsolicited AE has a partially missing start date and there is clear evidence about the last vaccination from the partially missing start date, then the start date is used to determine the last vaccination before the unsolicited. Situations may happen as:
 - o If the start date of AE has missing Day and non-missing Month and Year

- If the "Month/Year of vaccination (i) date" < "Month/Year of AE start date" < "Month/Year of vaccination (i+1) date", then it is clear that the last vaccination before this unsolicited AE is the vaccination i.
- If the "Month/Year of vaccination (i) date" < "Month/Year of AE start date" and there is no injection (i+1), then it is clear that the last vaccination before this unsolicited AE is the vaccination i.
- o If the start date of AE has missing Day and Month and non-missing Year:
- If the "Year of vaccination (i) date" < "Year of AE start date" < "Year of vaccination (i+1) date", then it is clear that the last vaccination before this unsolicited AE is the vaccination i.
- If the "Year of vaccination (i) date" < "Year of AE start date" and there is no injection (i+1), then it is clear that the last vaccination before this unsolicited AE is the vaccination i.
- If the start date is missing or partially missing (with no clear evidence about the last vaccination), or equal to any vaccination date, then the visit number in the "Appeared after Visit" or similar field, is used to determine the last vaccination before the unsolicited AE.

4.2.1.2.4 Time of Onset

Time of onset is derived from the start date of the unsolicited AE and the date of last vaccination as described in Section 4.2.1.2.3:

Time of Onset = start date of the unsolicited AE - date of last vaccination before the unsolicited AE + 1.

The time of onset is considered as missing only if one or both dates are missing or partially missing.

The unsolicited AEs will be analyzed "Within 30 days" after each vaccination, which corresponds to AEs with a time of onset between 1 and 31 days.

Unsolicited AE that occurred before vaccination (negative time of onset) will not be included in analysis but will be listed separately.

- For unsolicited AE with missing day, month and year, the unsolicited AE will be classified as "Within 30 days"
- For unsolicited AE with partially missing start date, the partial available information will be used to determine if this AE is classified "Within 30 days" or "Not within 30 days". An AE will be categorized as "Not within 30 days" only if there is clear evidence from

the partially missing start date that this AE happens before the first vaccination or after the last vaccination + 30 days. In all other situations, this AE is considered as "Within 30 days". Situations may happen as:

- o If the start date of AE has missing Day and non-missing Month and Year
- If the "Month/Year of AE start date" < "Month/Year of first vaccination date", then it is clear that this unsolicited AE happened before the first vaccination and this unsolicited AE will not be included in the analysis but will be listed separately.
- Else if the "Month/Year of last vaccination date" <= "Month/Year of AE start date" <= "Month/Year of (last vaccination date + 30 days)", then this unsolicited AE will be categorized as "Within 30 days".
- Else if the "Month/Year of AE start date" > "Month/Year of (last vaccination date + 30 days)", then this unsolicited AE will be categorized as "not within 30 days".
- o If the start date of AE has missing Day and Month and non-missing Year:
 - If the "Year of AE start date" < "Year of first vaccination date", then it is clear that this unsolicited AE happens before the first vaccination and this unsolicited AE will not be included in the analysis but will be listed separately.
 - Else if the "Year of last vaccination date" <= "Year of AE start date" <= "Year of (last vaccination date + 30 days)", then this unsolicited AE will be categorized as "Within 30 days".
 - Else if the "Year of AE start date" > "Year of (last vaccination date + 30 days)", then this unsolicited AE will be categorized as "not within 30 days".

A few examples of missing time of onset with start date of AE partially missing:

First injection	Last injection	Start date of the AE	Injection date + 30	Will be analyzed "Within 30 days"?
date	date			· · · · · · · · · · · · · · · · · · ·
16Oct2023	16Oct2023	Missing	N/A	Y
16Oct2023	16Oct2023	Sep2023	N/A	N
16Oct2023	16Oct2023	Oct2023	15Nov2023	Y
16Oct2023	16Oct2023	Nov2023	15Nov2023	Y
16Oct2023	16Oct2023	Dec2023	15Nov2023	N
05Jan2023	05Jan2023	2022	N/A	N
16Oct2023	16Oct2023	2023	15Nov2023	Y
08Dec2023	08Dec2023	2024	07Jan2024	Y
16Oct2023	16Oct2023	2024	15Nov2023	N

Time of onset period is displayed as D1-D4, D5-D8, D9-D15, D16 or later, and Missing.

4.2.1.2.5 **Duration**

Duration is derived from the start and end dates of the unsolicited AE:

Duration = End date of unsolicited AE – start date of unsolicited AE + 1.

The duration is considered as missing only if one or both of the start and end dates of the unsolicited AE is missing or partially missing.

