4 STUDY DESIGN

4.1 OVERALL DESIGN

This is a descriptive, Phase IV, open-label, single-arm, un-controlled, multi-center study to describe the immunogenicity and safety of a single dose of the MenACYW conjugate vaccine administrated as a booster vaccine in healthy toddlers 12 - 23 months of age who had been primed before study participation with at least 1 dose of another quadrivalent meningococcal conjugate vaccine, ie, Nimenrix[®] (MCV4-TT) or Menveo[®] (MCV4-CRM), in infancy.

The eligible participant population for this booster vaccine administration will be recruited in Argentina from the general population who have received at least one of the 2 infant doses of quadrivalent meningococcal conjugate vaccine (Nimenrix® or Menveo®) recommended at 3-months or at 5-months of age.

All participants will receive a single booster dose of the MenACYW conjugate vaccine at Visit 1 on Day (D)01.

All participants will provide a 5 mL blood sample for immunogenicity assessments at D01, prevaccination (baseline) and 1-month post booster vaccination at D31 (+14 days).

Solicited AE information will be collected for 7 days after booster vaccination; unsolicited AE information will be collected from Visit 1 (D01) to Visit 2 (D31 [+14 days]), and SAE information (including AESIs), will be collected throughout the study period from D01 to D31 (+14 days) after study vaccination.

The design of the study is summarized in Table 4.1.

Table 4.1: Overall design

Type of design	Open-label, single-group, multi-center
Phase	IV
Control method	Un-controlled
Study population	Healthy toddlers aged 12 months to 23 months
Level and method of blinding	Open-label
Study intervention assignment method	No randomization
Number of participants	A total of approximately 180 participants (minimum of 30 evaluable participants from the low - enrolling of the 2 priming vaccines) are expected to be enrolled with the aim to obtain a total of 150 evaluable participants.
Intervention groups	All eligible participants (12 – 23-month-old toddlers who had received at least one of two priming doses of either Nimenrix® or Menveo® vaccine during infancy as part of their recommended immunization, before 12 months of age) will be assigned in an open-label design to receive a single booster dose of the MenACYW conjugate vaccine with an interval of at least 2 months after the last vaccination with Nimenrix® or Menveo®, as an intramuscular (IM) injection at D01.

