8.3.1 Time Period and Frequency for Collecting AE and SAE Information

Immediate Post-vaccination Observation Period

Participants will be kept under observation for 30 minutes after vaccination to ensure their safety. The post-vaccination observation should be documented in the source document.

Reactogenicity

Solicited injection site reactions will be collected from the day of vaccination until 7 days after vaccination (D01 to D08).

Solicited systemic reactions will be collected from the day of vaccination until 7 days after vaccination (D01 to D08).

The solicited injection site reactions and systemic reactions that are pre-listed in the diary cards and CRF, together with the intensity scales, are presented in Appendix 10.2.5.1.1.

Unsolicited Non-serious Adverse Events

Unsolicited non-serious adverse events will be collected from the day of vaccination until 30 days after vaccination (D01 to D31 [+ 14 days]).

The intensity grading scale for unsolicited non-serious adverse events is presented in Appendix 10.2.5.1.2.

Adverse Events of Special Interest (AESIs)

AESIs will be collected throughout the study period from D01 to D31 (+14 days) post study vaccination.

See Section 8.3.6 for the list of AESIs.

SAEs

Information on SAEs will be collected and assessed throughout the study, from D01 to D31 (+14 days) post study vaccination. However, before the first study intervention administration, only SAEs related to study procedures are to be collected in the case report form (CRF) (eg, SAEs related to blood sampling).

All SAEs will be recorded and reported to the Sponsor or designee immediately and under no circumstance should this exceed 24 hours, as indicated in Appendix 10.2. The investigator will submit any updated SAE data to the Sponsor within 24 hours of it being available.

Investigators are not obligated to actively seek information on AEs or SAEs after conclusion of the study participation. However, if the investigator learns of any SAE, including a death, at any time after a participant has been discharged from the study, and he/she considers the event to be reasonably related to the study intervention or study participation, the investigator must promptly notify the Sponsor.

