Pre-vaccination temperature		X		
Review of temporary contraindications for blood sampling*	Х	X		X
Allocation of participant number	X	X		
Blood sampling (BL)† [5 mL]	X	BL0001 Pre-vac		BL0002
Vaccination (vac)	X	X		
Immediate surveillance (30 min)	X	X		
Diary card provided		X		
Collection of solicited injection site and systemic reactions	X	X	X	
Collection of unsolicited adverse events (AEs)	X	X	X	X
Diary card collected				X
Collection of concomitant medications	X Reportable concomitant medication	X	X	X
Collection of SAEs, including adverse events of special interest (AESIs)	X	To be reported at any time during the study from D01 to D31 (+14 days) after study vaccination		
End of Active Phase participation record‡	X			X

AESI: Adverse Events of Special Interest; CRF: case report form; SAE: Serious Adverse Events

^{*} Should a participant receive oral or injectable antibiotic therapy within 3 days prior to each blood draw, the Investigator will postpone that blood draw until it has been 3 days since the participant last received oral or injectable antibiotic therapy. Postponement is still to be within the timeframe for blood draw (30 to 44 days after vaccination at D01). If postponement will

result in the sample collection falling outside of the appropriate timeframe, the blood sample should be collected without postponement, and it should be documented appropriately that the sample was taken less than 3 days after stopping antibiotic treatment.

- † Blood sample at D01 will be drawn before administration of the vaccine
- ‡In case of participant discontinuation at a visit, the entire visit will be completed. Active Phase is from Visit 1 to Visit 2 completion.
- § The Investigator or an authorized designee will remind the parents, guardians, or legally acceptable representatives to bring back the diary card (DC) at the next visit and will answer any questions. If D09 falls on a weekend or holiday, the telephone call may be made on the following business day. During this telephone call, the staff will find out whether the participant experienced any SAEs (including AESIs) not yet reported and will remind the participant's parent/guardian to continue using the diary card, to bring the diary card to the study center at the next visit and confirm the date and time of the next visit.

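### The SAP's negative-onset test for pre-vaccination AEs does not fit its whole-date formula: day-before events score 0, and pre-injection events on D01 score 1

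*SAP*

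**What the plan says.** SAP 4.2.1.2.4 defines the derivation: "Time of Onset = start date of the unsolicited AE - date of last vaccination before the unsolicited AE + 1". The 30-day analysis takes events by that value, "which corresponds to AEs with a time of onset between 1 and 31 days". The exclusion is "Unsolicited AE that occurred before vaccination (negative time of onset) will not be included in analysis but will be listed separately". Onset is displayed in the categories D1-D4, D5-D8, D9-D15, D16 or later, and Missing.

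For an event dated on the vaccination day, SAP 4.2.1.2.3 uses a visit number to identify the last vaccination: if the start date is missing, unclear, "or equal to any vaccination date, then the visit number in the 'Appeared after Visit' or similar field, is used to determine the last vaccination".

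On timing, Protocol 4.1 states "All participants will receive a single booster dose of the MenACYW conjugate vaccine at Visit 1 on Day (D)01", and a footnote to SAP Table 1.2 states "Blood sample at D01 will be drawn before administration of the vaccine". Protocol 8.3.1 limits what is recorded earlier: "before the first study intervention administration, only SAEs related to study procedures are to be collected in the case report form (CRF", with blood-sampling events as its example. Protocol 10.2.2 classes SAEs as unsolicited AEs, so the onset rule applies to them. SAP 4.2.1.2.6 reports SAEs within 7 days, within 30 days and during the study; the last period has no onset limit.

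**The concern.** The intent is plain: events that began before the vaccine was given should be listed apart and not counted as post-vaccination events. The operational test is the sign of a derived number, and that number does not turn negative where the intent requires it.

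Two kinds of event are affected, for different reasons. An event starting the day before vaccination falls in a gap, neither counted within 30 days nor sent to the listing. An event on D01 before the injection is counted as post-vaccination. The second kind matters more here, because consent, the first blood draw and vaccination all take place at Visit 1, and a procedure-related SAE from that blood draw is the pre-vaccination event the protocol explicitly asks sites to record.

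At stake is the SAE and unsolicited AE description of a study with safety as a stated objective. SAEs are likely to be so few that one misplaced child changes the reported figure. SAP 3.4.3 also presents the SAE overview by priming vaccine, where the denominators are smaller.

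**Working it through.** **Inputs.** Formula, exclusion rule and window from SAP 4.2.1.2.4; same-day rule from SAP 4.2.1.2.3; vaccination and first blood draw both on D01 (Protocol 4.1, SAP Table 1.2). The vaccination date 16 October 2023 is taken from the SAP's own example table.

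**Reproducing the plan's window.** Onset = (start − vaccination) + 1.
- Start 16 October: 0 + 1 = 1.
- Start 15 November: 30 + 1 = 31.

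This matches the stated 1 to 31 days. All nine rows of the SAP's partial-date table also reproduce.

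**Applying the exclusion rule.**

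| Start of event | Onset | Negative? | In 1 to 31? | Result as written |
|---|---|---|---|---|
| 14 October | −2 + 1 = −1 | yes | no | listed separately, as intended |
| 15 October | −1 + 1 = 0 | no | no | not in the 30-day table; no listing rule, no display category |
| 16 October, before injection | 0 + 1 = 1 | no | yes | counted within 30 days |
| 16 October, after injection | 0 + 1 = 1 | no | yes | counted within 30 days, as intended |

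The third and fourth rows cannot be told apart by the formula.

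**What causes what.** Without the added day, the 15 October event scores −1 and is listed, so the +1 explains that row. The pre-injection D01 event then scores 0, which is still not negative. Its cause is the use of whole dates, and only a recorded before/after item or a clock time can resolve it.

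**Other rules that might separate the D01 event.** The same-day rule relies on a visit number, and blood draw and injection are both at Visit 1. If the event were treated as having no preceding vaccination, the formula would lack a date and onset would be missing, not negative. The SAP does not say what follows.

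**Consistency within the section.** For partial dates, the same section tests whether the start month or year is earlier than that of vaccination. Only the rule for complete dates relies on the sign of a value that has had 1 added.

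**Illustrative size.** The number vaccinated is not stated, so 150 is an assumption, and 30 is an assumed small priming-vaccine group. Clopper-Pearson 95% limits: for 0/n the upper limit is 1 − 0.025^(1/n); for 1/n the lower limit is 1 − 0.975^(1/n), and the upper limit solves (1−p)^n + np(1−p)^(n−1) = 0.025.
- n = 150: 0/150 gives 0 to 2.43%; 1/150 = 0.67% gives 0.02 to 3.66%.
- n = 30: 1/30 = 3.3% gives 0.08 to 17.2%.

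These show the effect of one hypothetical event. The documents give no frequency for such events.

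**The case against.** The strongest reply is that the governing words are that the event occurred before vaccination, and the bracketed phrase only glosses them. A careful programmer would honour the intent. Same-day events also have their own route, the visit field or a similar one, and the CRF is not in the documents, so its failure cannot be shown. That stands. A reader might infer that every same-day pre-vaccination event will be misclassified. The documents support only that the text, as described, does not clearly separate such events.

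A reader might also infer that the added day causes the D01 problem, or that onset-0 events enter the 30-day table. Neither is so: the D01 event escapes with or without the +1, and 0 is already outside 1 to 31.

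The affected set is very small. Before vaccination only procedure-related SAEs are collected, and a child with a serious event from the blood draw must still be vaccinated to enter the safety set. Onset 0 should be rare when all procedures are on D01. It is not impossible: Protocol 10.2.2 counts as AEs conditions detected after vaccination even if present earlier.

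Safeguards exist too. Protocol 10.2.3 lets the investigator class an event that started before vaccination as not related, and for SAEs the relationship to study procedures is assessed by both investigator and sponsor. SAP 4.2.2.4 shows that relationship, but only in the listing. These protect the causality-based results and leave the all-causality counts exposed.

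**Conclusion.** The exclusion rule is wrong as written, with very small expected impact. Day-before events have no assigned place: they stay out of the 30-day table but are not listed as pre-vaccination, and a serious one could still enter the during-study SAE count. Applied literally, the formula counts pre-injection D01 events as within 30 days, and nothing else described in the SAP clearly prevents this.

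The effect is confined to all-causality counts and leans towards over-counting. Few events, possibly none, are expected. One SAE among an assumed 150 vaccinated would appear as 0.67% instead of 0%. A larger denominator of 180 is not a suitable illustration, because SAP section 5 says recruitment stopped before that number. The conclusion on D01 events assumes that the CRF holds no further item recording order relative to the injection that the SAP already intends to use.

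**What to change.** In SAP 4.2.1.2.4, replace the bracketed words on negative onset with: *start date before the vaccination date (time of onset ≤ 0), or start date equal to the vaccination date with onset recorded as before the injection*. Put these events in the separate listing and keep them out of the within-7-day and within-30-day tables. State whether serious ones count in the during-study row, since that row takes all SAEs. Where same-day order is unknown, count the event as post-vaccination, which keeps the conservative default.

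Changing the test to ≤ 0 alone would repair the day-before case and leave D01 unchanged. The SAP should therefore also name the CRF field or source item that establishes order on D01.

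The cost is one sentence, a small programming change, and a check of D01-onset events against the CRF or source. If the CRF has no before/after item, that check must be made from source documents; with so few events the work should be slight.

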4.2.1.2.6 Serious Adverse Events

An event will be considered as a serious event if "Yes" is checked for "Serious" in the CRF. SAEs will be analyzed throughout the study using the following periods:

- Within 7 days
- Within 30 days
- During the study (i.e., all SAEs occurred during the study)

4.2.1.2.7 Adverse Events of Special Interest

An event will be considered as an AESI if "Yes' is checked for "Is the event an AESI?" in the CRF.

AESIs will be analyzed throughout the study using the following periods:

- Within 7 days
- Within 30 days
- During the study (i.e., all AESIs occurred during the study)

4.2.2 Other Safety Endpoints

4.2.2.1 Action Taken

This information will be summarized as collected, including missing observations. No derivation or imputation will be done.

4.2.2.2 Seriousness

This information will be summarized as collected. No derivation or imputation will be done.

4.2.2.3 Outcome

This information will be summarized as collected. No derivation or imputation will be done.

4.2.2.4 Causal Relationship

This information will be summarized as collected in the field "Relationship to study vaccine". Missing causal relationship will be handled as described in Section 3.4.5.1.2. Relationship to study procedure is only presented in the listing.

4.2.2.5 Adverse Events Leading to Study Discontinuation

This information will be summarized as collected. A flag is available in the clinical database for all AEs in order to identify AEs leading to discontinuation before the end of active phase. In general, the items that are counted are:

- Disposition table: A participant who, on the "Completion at End of Study" form question "What was the participant's status?" has "Adverse Event" checked.
- Safety overview table: A participant who has either on the "Completion at End of Study" form, question "What was the participant's status?" has "Adverse Event" checked or lists a solicited AE that has "Caused Study Termination" checked that is at least Grade 1 or an unsolicited AE that has "Caused Study Discontinuation" checked that is at least Grade 1 or missing and is within the time period indicated.
- System Organ Class (SOC)/Preferred Term (PT) table: A solicited AE that has "Caused Study Termination" checked that is at least Grade 1 or an unsolicited AE that has "Caused Study Discontinuation" checked that is at least Grade 1 or missing and is within the time period indicated.

